Different risk assessment tools have been proposed for patients undergoing AHA(11)(12). The APACHE-II score, even though developed for critical care, seems to be the one with best prediction of outcome. Risk assessment tools are important to support clinical decision making by the perioperative team as subjective clinical assessment often underestimates the risk for the patients in highest risk of complications and death(13). Good clinical decision-making is likely to improve the clinical outcome by allocating appropriate resources. Prognostic tools are also useful to inform patients about what to expect in the immediate postoperative phase and of long-term outcome. Especially in the elder population with increased risk of long hospitalisation and loss of function or independency this can be useful to give informed consent to treatment strategy. Furthermore, good risk assessment is

important to optimize palliative care after end-of-life decisions, which is often ignored in research, but highly relevant in clinical work.

During recent years use of prognostic biomarkers in other high mortality populations have received much attention for risk stratification(14). An ideal biomarker should be readily available upon decision-making, easy to measure, reliable and biologically stable. Furthermore it has to be able to accurately differentiate prognosis for patients to have value in the clinical decision-making and guide the treatment of the patient. It should be linked to the clinical outcomes.

We aim to identify serological AHA biomarkers that are prognostic or predictive for postoperative morbidity, mortality and length of hospitalisation.

Potential biomarkers:

Inflammation markers:

Soluble urokinase-type plasminogen activator receptor (SUPAR) is a relatively new potential biomarker for inflammation. It is related to mortality in critically ill patients(15) especially in combination with the APACHE II score(16)(17). SUPAR is thought to be related to the inflammation reaction and endothelial dysfunction affected in critically ill patients(18). It is furthermore related to cardiovascular disease and subclinical organ damage(19) and is shown to be relatively stable throughout the day without circadian variations. It is related to all-cause mortality in major cohorts from different parts of the world(20). It has been suggested that the biomarker can be used to strengthen risk stratification for patients presenting acutely at the emergency department(21).

IL-10, IL-6, Tumor Necrosis Factor alpha, IP-10 are other markers of inflammation that regulate the inflammatory response to disease. It is proposed that increased synthesis or reduced metabolism of IL-6 is related to poor outcome in sepsis(22).

Troponin:

Troponin is a well-established biomarker for myocardial infarction. Recent studies show that it is related to the APACHE II score and could be useful as a biomarker for overall mortality in critically ill patients with severe sepsis(23)(24)(25).

Endothelial dysfunction

Markers of endothelial function have been suggested to predict poor outcome. Syndecan-1, a transmembrane endothelial proteoglycan, which in serum is a marker of glycocalyx degradation, is related to mortality in trauma patients(27).

Endocrine and other markers

The endocrine system is highly involved in the surgical stress response and imbalances in hormonal response to stress could potentially predict outcome. Especially catecholamines are involved in the inflammatory response and related to endothelial dysfunction(27).

Furthermore, combination of different molecular biomarkers could be of interest to create the best possible molecular risk assessment tool(14).

Methods

Manuscripts will be prepared using the STROBE-ME statement guidelines(29).

Approvals and ethical considerations:

Danish legislation “Lov om behandling af personoplysninger” will be followed and the study will be reported to the Danish Data Protection Agency.

Data used in these studies are collected in the quality improvement program “Acute High-Risk Abdominal Surgery study – an optimized Perioperative Course (AHA)” (ClinicalTrials.gov Identifier: NCT01899885) approved by the Danish Data Protection Agency (jr.no. 2007-58-0015) **HVH-2013-052** in 2013. In this program patients were enrolled in a standardized protocol of perioperative optimization. The standardized protocol included collection of blood samples for future research.

Patients were informed about the AHA protocol and gave informed consent where possible. If patients were in a state where informed consent was not possible informed consent was sought from relatives.

As this was a qualitative improvement programme, it did not require approval by an ethical committee according to Danish law. Blood samples were drawn and collected with the standard preoperative tests and stored at -80C in a biobank.

We will establish a new research bio bank based on material from the samples collected in relation to the standard treatment according to the AHA-protocol (one EDTA-tube and one tube with coagulation enhancer). The research biobank will be reported to the Danish Data Protection Agency. After approval the biological material will be kept in the research biobank until the end of the study, at which time the samples have been used entirely or will be transferred back to the biobank from which they originally were taken. The present study is expected finalized by May 1, 2022.

Analysis of the samples from the biobank will require approval by the Ethics Committee including dispensation from obtaining consent from involved patients. Retrospective consent is impossible to obtain as a large proportion of patients have died since the data collection started, and analysis of the data set without the patients, who have died is worthless as a predictive tool. Research on this vulnerable population with high mortality and morbidity is very limited. It is therefore an important ethical aspect that the collected data can be used for research, which may be beneficial for future critically ill, emergency patients.

Approval for these studies will be applied from the Ethics Committee of the Capital Region of Denmark. Referral of data from the AHA quality improvement project to this study will be registered and approved by the Danish Data Protection Agency. The biological material and non-anonymous data, from both the research bio bank and the samples collected in relation to standard treatment, will be destroyed when the approval from the Danish Data Protection Agency expires.

We will search the national register for usage of biological tissue, “Vævsanvendelsesregistret”, for patients who only wish their tissue is used for their own treatment. Samples from these patients will not be included in this project.

Risks, side effects and harms

Potential harms for the participants are limited as the research is focused on preoperative risk assessment and not long-term prediction of future diseases. There is therefore a low risk of findings that may affect the participants. The biomarkers we wish to study have in similar studies of critically ill patients not shown any random findings affecting the participants.

Population

We will include patients with a preoperative blood sample stored in the bio bank; the patients did undergo AHA at Hvidovre Hospital, Copenhagen, Denmark, from June 1st 2013 when the AHA study protocol was initiated.

Inclusion criteria were: Patients aged 18 or older with the suspicion for abdominal pathology requiring immediate emergency laparotomy or laparoscopy including reoperations after elective surgery and reoperations after previous AHA surgery.

We excluded the following procedures: appendectomies; negative laparoscopies and laparotomies; cholecystectomies; simple herniotomies following incarceration (without intestinal resection); reoperation due to fascial separation with no other abdominal pathology; internal herniation after roux-en-y gastric bypass surgery; sub-acute surgery (planned within 48 hours) for inflammatory bowel disease; and sub-acute colorectal cancer surgery.

We excluded, traumas, pregnant woman, uro-genital, gynaecological and vascular pathology except for mesenteric ischemia.

Data collection

Data on mortality was obtained using the Danish Civil Registration System(30). This register is maintained by the Danish government and assigns a unique personal identification number to all Danish citizens. It contains data on address, immigration emigration, gender, date of birth and exact day of death. It is updated within days of any change in information.

Other data were collected in the medical records of patients. Complications were defined using the Clavien-Dindo Classification for Surgical Complications(31).

Outcome measures

Primary outcomes are short and long-term mortality (30 days and 180 days respectively) and major complications during index hospitalization (Clavien-Dindo >2). Secondary outcomes are length of hospitalisation, length of intensive care admission as well as perioperative need for inotropic or vasopressor support and high volume fluid resuscitation.

Description of biological material

Blood samples were collected at the time of induction of anaesthesia. For AHA-patients a pre-operative optimisation protocol was introduced in the hospital throughout the data collection period, which stated that the patient was optimized with goal directed fluid therapy before induction of anaesthesia. The blood samples were usually taken from the arterial line used for invasive blood pressure monitoring but some were obtained from venous puncture with standard preoperative tests.

The blood samples were collected in tubes with EDTA as anti-coagulant for plasma and in tubes with coagulation enhancer for serum. After centrifugation for 10 mins at room temperature the plasma and serum, respectively were transferred to freezing tubes for subsequent long-term storage at -80C.

Biochemical analysis

A predefined biochemical analysis protocol for each biomarker will be followed. The methods used will be described in the specific published studies.

Statistical analysis protocol

Data will be analysed using the SPSS, STATA, R or SAS software. Tests will be two-sided with $p<0.05$ considered to be significant.

Missing data will be assessed using Little's test for data missing completely at random(32). If data is not missing completely at random multiple imputation will be performed(33).

All patients or random samples (with a size defined by a preoperative sample size estimation) from the AHA cohort with blood samples taken preoperatively will be included in the analysis. Baseline characteristics will be presented and for biomarkers with continuous data patients will be stratified into quartiles or tertiles. Characteristics of populations will be presented as frequencies for categorical variables and medians with inter-quartile range for continuous variables. Differences between groups will be presented using appropriate statistical tests. Kaplan-Meier curves will be produced for the primary outcomes and compared using the log-rank test. COX-regression will be used to perform multivariate analyses adjusted for potential confounders with Bonferroni correction.

Receiver operating characteristic curves for each biomarker will be produced for the primary outcomes. Area under the curve will be measured to evaluate the prognostic value of the biomarkers.

Limitations of the study

Data collection during clinical work including blood samples requires resources and is susceptible to selection and information bias. It is possible that resources for collecting blood samples correctly were reduced for the most unstable patients at the time of induction of anaesthesia. Patients who were considered too frail to undergo surgery, where a palliative or conservative approach was chosen, were not included in this study. Postoperatively, patients in the AHA-cohort were assigned to postoperative intensive monitoring in the post-operative care unit if they had American Society of Anaesthesiologist physical performance score(34) above two. This stratification is susceptible to information-bias because of inter-observer variation(35).

The data is collected in a single medical facility with an optimized care protocol for AHA and can therefore not uncritically be applied to other populations.

Economical support and budget:

The clinical study as well as establishment of the biobank has been supported by a grant from the Capital Region of Denmark (Region H). The cost of biochemical analysis will be covered by the Department of Clinical Biochemistry, Hvidovre Hospital. Other expenses will be covered by the AHA research group, Department of Anaesthesiology and Intensive Care and Department of Surgical Gastroenterology, Hvidovre Hospital.

Publication of results:

Results from the studies will be published in medical journals indexed in the PubMed/EMBASE database.

References

2. Tolstrup M-B, Watt SK, Gögenur I. Morbidity and mortality rates after emergency abdominal surgery: an analysis of 4346 patients scheduled for emergency laparotomy or laparoscopy. *Langenbeck's Arch Surg*. 2016 Aug 9
4. Jeppesen MH, Tolstrup M-B, Kehlet Watt S, Gögenur I. Risk factors affecting morbidity and mortality following emergency laparotomy for small bowel obstruction: A retrospective cohort study. *Int J Surg*. 2016 Apr;28:63–8.

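### If catecholamines are assayed, drug given before the induction sample could be read as stress hormone, and support already running could count in both marker and outcome; the extent is unknown

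*Combined protocol and SAP*

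**What the plan says.** Under the potential biomarkers, the paragraph on endocrine and other markers gives the rationale that "imbalances in hormonal response to stress could potentially predict outcome" and then singles out one class: "Especially catecholamines are involved in the inflammatory response and related to endothelial dysfunction". No analyte or assay is named. The section on biochemical analysis refers to a predefined protocol for each biomarker, which is not part of the document.

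On timing, the description of biological material says "Blood samples were collected at the time of induction of anaesthesia". Most samples came from the arterial line, but "some were obtained from venous puncture with standard preoperative tests". The only treatment before sampling that is described is fluid: "the patient was optimized with goal directed fluid therapy before induction of anaesthesia".

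The exclusions under Population concern type of procedure ("We excluded the following procedures: appendectomies; negative laparoscopies and laparotomies; cholecystectomies" and others), trauma, pregnancy and certain pathologies. None concerns drug treatment at sampling.

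The secondary outcomes include "perioperative need for inotropic or vasopressor support and high volume fluid resuscitation", with no start time relative to the blood sample.

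In the statistical analysis protocol, the sentence that sets who enters the analysis begins "All patients or random samples (with a size defined by a preoperative sample size estimation) from the AHA cohort with blood samples taken preoperatively will". The section plans quantile groups, Kaplan-Meier curves, Cox models adjusted for confounders that are not named, and an ROC curve for each biomarker against the primary outcomes.

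**The concern.** The stated purpose is to learn whether the patient's own hormonal response carries prognostic information. Some inotropes and vasopressors are themselves catecholamines. Where the infused drug and the assayed hormone are the same molecule, as with noradrenaline or adrenaline, the measured level is the sum of the two. Patients treated in this way before the sample would tend to fall in the top quantile group because they were being treated, which the clinical team already knows.

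Two things are at stake. The first is interpretation: an association with death could be credited to the stress response when part of it reflects treatment under way. The second is circularity: if support already running at sampling counts towards the support outcome, the same drug exposure raises the marker and satisfies the outcome.

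**Working it through.** The plan gives no figure to reproduce: no sample size, event rate or frequency of drug support. The check therefore has two parts, a reading of the text and an illustration of scale.

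**Reading the text**

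1. Is the marker meant to be endogenous? Yes, by the rationale in the biomarker section.
2. Could a drug precede the sample? Sampling is at induction, and the cohort is emergency surgery including reoperations. The limitations section speaks of the most unstable patients at induction. Support is expected often enough to be listed as an outcome. None of this shows that it began before sampling; the text neither describes this nor rules it out.
3. Does anything in the analysis separate exposed patients? There is no exclusion, named covariate, stratum or sensitivity analysis for it, and the limitations section does not mention it.
4. Would an unnamed confounder cover it? Not fully. The ROC and Kaplan-Meier analyses are described without adjustment, and a covariate in a Cox model does not alter how the support outcome is counted.

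**Scale, with assumed inputs**

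Assume that a share *e* of patients is on a catecholamine drug at sampling, that all of them read above every other patient, and that the level carries no prognostic information within either group. Assume 30-day mortality of 45% in exposed and 15% in unexposed patients. All of these are assumptions.

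*Top quartile.* The exposed share is *e*/25%.
- *e* = 5%: 5/25 = 20%. Mortality = 0.20 × 45% + 0.80 × 15% = 21%.
- *e* = 15%: 15/25 = 60%. Mortality = 0.60 × 45% + 0.40 × 15% = 33%.
- Lower three quartiles: 15% in both cases.

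*AUC.* Let f1 and f0 be the exposed shares among patients with and without the outcome. A random pair is ranked correctly with probability f1(1 − f0) + ½[f1·f0 + (1 − f1)(1 − f0)], which simplifies to AUC = 0.5 + (f1 − f0)/2.
- *e* = 5%: f1 = 0.0225/(0.0225 + 0.1425) = 13.6%; f0 = 0.0275/(0.0275 + 0.8075) = 3.3%; AUC ≈ 0.55.
- *e* = 15%: f1 = 0.0675/(0.0675 + 0.1275) = 34.6%; f0 = 0.0825/(0.0825 + 0.7225) = 10.2%; AUC ≈ 0.62.

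Setting f1 and f0 directly shows the wider range:

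| f1 | f0 | AUC |
|---|---|---|
| equal to f0 | any | 0.50 |
| 10% | 2% | 0.54 |
| 30% | 5% | 0.625 |
| 50% | 10% | 0.70 |

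Under the same assumptions, an analysis restricted to unexposed patients returns 15% mortality in every quartile and an AUC of 0.50, so the comparison would reveal the artefact.

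*Support outcome.* If every drug exposure at sampling counts as support, no patient without the outcome is exposed, so f0 = 0 and AUC = 0.5 + f1/2. Here f1 is the share of supported patients whose support was already running. For f1 = 10%, 30% and 50%, the AUC is 0.55, 0.65 and 0.75, by construction alone.

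**The case against.** The other side has several good points.

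- Catecholamines are only a potential class, covered in a few lines. They may never be assayed, and the protocol for each biomarker, which is not available here, may deal with sampling conditions. This stands, and the point is conditional for that reason. But where drug and hormone are the same molecule, assay procedure alone cannot separate them, so an analysis rule is still needed.
- No text shows exposure before sampling. Fluid therapy is the only treatment described, some samples were venous and taken with routine preoperative tests, and the limitations section suggests that unstable patients may be under-sampled. This stands: the size could be zero.
- Whether a drug raises the reading depends on drug and analyte, neither of which is specified. This stands. A reader might infer that the assay would record drug instead of hormone. The documents do not support that; the supportable statement is that the two could be mixed.
- A level raised by drug may still predict death in this cohort, and the plan seeks prognostic markers. This stands: the association would be real as prediction. What is at risk is its attribution to the hormonal response and its value beyond what the team already knows.
- The plan assigns Kaplan-Meier and ROC analyses to the primary outcomes and does not say how the support outcome will be related to each marker. The circularity therefore arises only if that analysis is done, but support is a declared outcome and the definition should be settled first.
- Excluding exposed patients from the main analysis would remove some of the sickest. This also stands and shapes the fix.

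**Conclusion.** The point holds in conditional form. If catecholamines are assayed, including all patients sampled at induction could mix administered drug with the endogenous response that the marker is meant to represent, and the undated support outcome could share its exposure with the marker. The plan contains nothing that would reveal either problem.

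The size is unknown. The illustrative AUCs rest on assumed exposure and mortality, complete separation of exposed from unexposed levels, and no endogenous prognostic value; these last two are extreme. With no exposure, or exposure unrelated to outcome, the effect on the primary-outcome AUC is nil.

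A reader might go further and infer that exposed patients must be excluded from the main analysis, or that vasopressor exposure should be a covariate for every other marker. The documents support neither. Exclusion selects on severity in a cohort that may already under-represent unstable patients, and the mixing described here concerns catecholamine levels only. The change is still worth making: it is cheap, and a named confounder alone would correct neither the unadjusted ROC nor the circular outcome.

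**What to change.** Add to the statistical analysis protocol, for catecholamine markers only and before assay results are seen:

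1. Where the records allow, flag whether a catecholamine drug was being given, or had just been given, when the blood was drawn. Define the time window in advance, and report how many patients cannot be classified.
2. Keep the full-cohort analysis as planned.
3. Pre-specify a sensitivity analysis restricted to unexposed patients, repeating the quantile comparison, Cox model and ROC curve. Report exposed patients separately, with their number and outcomes.
4. When relating catecholamine level to inotropic or vasopressor support, count only support that started after the blood sample.

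The cost is modest record extraction and a smaller unexposed subset with less precision. The protocol says that clinical data came from medical records but does not say that drug start times or exact sampling times were captured, so feasibility should be checked first. Nothing in patient care changes.

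### Little's test decides whether missing data are imputed, and no method is named if it does not reject; fix the main missing-data method in advance

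*Combined protocol and SAP*

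**What the plan says.** The Statistical analysis protocol has two sentences on missing data. The first is "Missing data will be assessed using Little's test for data missing completely at random"; the second is "If data is not missing completely at random multiple imputation will be performed". Nothing in the document says what is done otherwise. No imputation model, list of variables, number of imputations or sensitivity analysis is given.

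Four other statements bear on the point:

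- The same section leaves the size of each analysis set open: "All patients or random samples (with a size defined by a preoperative sample size estimation").
- It then says "COX-regression will be used to perform multivariate analyses adjusted for potential confounders with Bonferroni correction". The confounders are not listed.
- Under Population, "We will include patients with a preoperative blood sample stored in the bio bank".
- Under Data collection, "Data on mortality was obtained using the Danish Civil Registration System", whereas "Other data were collected in the medical records of patients". Covariates and major complications (Clavien-Dindo >2, one of the primary outcomes) therefore come from records, and death comes from a register.

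**The concern.** A significance test on the study data chooses the missing-data method, and one of its two branches is blank. There are four difficulties.

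1. Failing to reject MCAR is not evidence for MCAR. In a small set with few gaps the test has little power, and low power would be taken as permission not to impute.
2. Whether the test rejects depends on n and on the variables entered. Both may differ between the biomarker analyses, so the same mechanism could be handled in two ways.
3. Rejection does not by itself justify standard imputation, because the test cannot separate missing at random from missing not at random. That assumption has to be stated whatever the test shows.
4. Even under MCAR, a complete-case Cox model drops every patient with any covariate gap. Passing the test is therefore no reason to leave imputation out.

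At stake are the consistency and precision of the adjusted Cox models and, under some patterns of missingness, their bias. Unadjusted Kaplan-Meier, log-rank and ROC analyses of mortality use no covariates, so covariate gaps do not touch them.

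**Working it through.** The plan has no figure to reproduce. All inputs below are assumptions, except the 5% level, which is the plan's general threshold and is taken to apply to Little's test.

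**How often the test rejects when MCAR is false, one incomplete variable.** Assume 20% deaths, 5% missing in survivors, and odds of missing doubled in deaths.

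- Missing in deaths: odds 2 × 0.05/0.95 = 0.1053, so the probability is 0.1053/1.1053 = 0.0952.
- Overall missing fraction: m = 0.2 × 0.0952 + 0.8 × 0.05 = 0.0590.
- Death rate among patients with the gap: 0.2 × 0.0952/0.0590 = 0.3226. Among the others: 0.2 × 0.9048/0.9410 = 0.1923. Difference: 0.1303.
- Noncentrality = n × m × (1−m) × 0.1303²/(0.2 × 0.8), which is 1.77 at n=300 and 5.89 at n=1000.
- Degrees of freedom = number of fully observed variables entered, death included.

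Chance of rejection, with the same steps for 2% and 8% missing in survivors:

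| Missing in survivors | n | 10 variables | 5 variables | 1 variable |
|---|---|---|---|---|
| 2% | 300 | 7% | 9% | 14% |
| 2% | 1000 | 14% | 19% | 36% |
| 5% | 300 | 11% | 14% | 27% |
| 5% | 1000 | 32% | 43% | 68% |
| 8% | 300 | 15% | 20% | 37% |
| 8% | 1000 | 48% | 61% | 84% |

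The mechanism is fixed within each missing fraction. Only n and the number of variables entered change whether imputation would be used.

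**Patients lost to complete-case analysis.** With eight covariates each missing independently under MCAR, the loss is 1 − 0.98⁸ = 14.9% at 2% and 1 − 0.95⁸ = 33.7% at 5%. If the gaps fall in the same patients, the loss is 2% or 5%.

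**Bias in the adjusted biomarker coefficient.** These are simulated Cox models with n=1000, eight correlated covariates, true log hazard ratio 0.5, 20% deaths by day 180, 5% missing and odds doubled. The range covers separate runs of 100, 150 and 300 datasets where more than one was made.

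| Gaps depend on | Overlapping gaps | Independent gaps |
|---|---|---|
| Death only | about 0.00 (+0.002, +0.003) | +0.03 to +0.04 |
| Death with above-average biomarker | −0.007 to −0.015 | −0.09 to −0.10 |

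In the 100-dataset run, imputation that included the event indicator and cumulative hazard gave coefficients within about 0.006 of the full-data value in all four cells. In the pattern of the second row, simulated Little's tests rejected in 18-19% of datasets at n=300 and 40-47% at n=1000 (simulation error up to 3 points). The test would thus miss this pattern more often than not.

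**Precision under MCAR, 5% missing, n=300.** The median standard error, complete-case against imputed, was 0.204 v 0.160 (ratio 1.27) with independent gaps and 0.1658 v 0.1633 (ratio 1.02) with overlapping gaps.

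**The case against.** The strongest reply is that the harm is not demonstrated. Every magnitude rests on assumed inputs. Material bias appears only when eight covariates have independent gaps, a near-worst case that discards more than a third of patients. Even there the shift of about −0.09 is less than one complete-case standard error (about 0.12). With overlapping gaps it is negligible. This stands, and it limits the weight of the point.

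Two further limits stand. A stored sample does not guarantee every assay value, since the biobank description mentions two tube types and samples that may be used up, so gaps are not confined to record covariates. Also, major complications come from records and may have gaps of their own, so a remedy built only around time to death would be incomplete.

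It can also be said that preferring imputation is a matter of taste. That is less convincing: the plan already accepts multiple imputation, and complete-case results would still be reported.

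A reader might infer three stronger things that the documents do not support:

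- That the plan prescribes complete-case analysis when the test does not reject. That is the likely default, but it is not stated.
- That the mortality outcome itself is compromised. Deaths come from a register updated within days.
- That the remark under Limitations of the study, on sample collection in the most unstable patients, shows informative missing data within the analysis set. Patients without a stored sample are not included, so this is a problem of selection into the study. Neither the present rule nor the change proposed here solves it.

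**Conclusion.** The point holds in a limited form. The plan lets a test of MCAR choose the method and leaves one branch undefined, so the main analysis of the adjusted models is not fixed in advance and could differ between biomarker papers for reasons of sample size alone.

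The size cannot be derived from the documents. Under the stated assumptions, complete-case bias is under 0.02 on a coefficient of 0.5 if gaps overlap. If they are independent, it is about +0.03 to +0.04 (gaps depending on death only) or −0.09 to −0.10 (death and high biomarker). Under MCAR only precision is lost. This is an improvement worth making, not a flaw that undermines the study.

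**What to change.** - Remove Little's test as the trigger for imputation; it may be reported descriptively.
- Report the proportion missing for each variable, including assay values and complications.
- Pre-specify multiple imputation, under a stated missing-at-random assumption, as the main analysis for adjusted models with incomplete variables.
- Include in the imputation model the biomarker, all covariates of the analysis model and the outcome being analysed: event indicator and cumulative hazard for mortality, and the complication indicator for Clavien-Dindo >2, which may itself need imputing.
- Report the complete-case analysis as a sensitivity analysis.

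The cost is a few sentences in the plan and modest extra analysis work. The main analysis then relies on missing at random, which the data cannot confirm. If missingness proves trivial, the two analyses will nearly agree and little is gained.

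### The natural reading of the survival comparison is an unordered test on quartiles or tertiles, and the marker's form in the Cox model is not stated; prespecifying a continuous term and a trend test is a cheap improvement

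*Combined protocol and SAP*

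**What the plan says.** All the relevant text is in the Statistical analysis protocol section of the combined protocol and SAP.

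- **Grouping.** In the sentence on baseline characteristics, "for biomarkers with continuous data patients will be stratified into quartiles or tertiles". The choice between four and three groups is left open.
- **Survival comparison.** "Kaplan-Meier curves will be produced for the primary outcomes and compared using the log-rank test". The groups behind the curves are not named here, and no ordered or trend version of the test is mentioned.
- **Adjusted model.** "COX-regression will be used to perform multivariate analyses adjusted for potential confounders with Bonferroni correction". The coding of the marker, grouped or continuous, is not given.
- **Discrimination.** "Receiver operating characteristic curves for each biomarker will be produced for the primary outcomes", with the area under the curve as the measure of prognostic value.
- **Significance level.** "Tests will be two-sided with $p<0.05$ considered to be significant".
- **Size.** "All patients or random samples (with a size defined by a preoperative sample size estimation) from the AHA cohort". No number of patients or events, effect size or power is stated.

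**The concern.** The quantile groups are the only grouping the plan names, so the curves are most naturally read as drawn by quartile or tertile. The standard k-group log-rank test has k − 1 degrees of freedom and gives the same result however the groups are ordered. For a marker whose risk rises steadily with concentration, power is then lost in two ways. Differences within a group are ignored, and degrees of freedom are spent on patterns that nobody expects.

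The study aims to identify prognostic markers, so a true marker could look unconvincing on its survival curves. Leaving both the number of groups and the Cox coding open also means that the form of the main adjusted result could be chosen after the data are seen.

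**Working it through.** The plan states no power or sample size, so there is no figure of its own to reproduce. The check asks what the grouped test would cost under stated assumptions.

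**From the plan:** two-sided α = 0.05; four or three groups; log-rank test with no trend version.

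**Assumed:** marker normal after log transformation; hazard log-linear in the log marker; equal-sized groups; power of the continuous 1-df test varied from 50% to 99%.

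**Step 1: information kept by grouping.** For a standard normal marker cut at quantiles c₀,…,c_k, the group means are m_j = k[φ(c_{j−1}) − φ(c_j)]. The share of variance kept is the average of m_j².
- Quartiles: means ±1.271 and ±0.325; share (1.271² + 0.325²)/2 = 0.861.
- Tertiles: means ±1.091 and 0; share 2 × 1.091²/3 = 0.793.

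**Step 2: non-centrality.** For the continuous test, λ = (z₀.₉₇₅ + z_power)². At 80% power this is (1.960 + 0.842)² = 7.85. After grouping it is 7.85 × 0.861 = 6.76 for quartiles and 7.85 × 0.793 = 6.23 for tertiles.

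**Step 3: power** from the non-central chi-square with 3 or 2 df. Loss in percentage points is in brackets.

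| Continuous, 1 df | Quartiles, 3 df | Tertiles, 2 df |
|---|---|---|
| 50% | 30.0% (20.0) | 32.6% (17.4) |
| 70% | 46.5% (23.5) | 49.5% (20.5) |
| 80% | 57.3% (22.7) | 60.1% (19.9) |
| 90% | 71.4% (18.6) | 73.6% (16.4) |
| 95% | 81.1% (13.9) | 82.8% (12.2) |
| 99% | 93.1% (5.9) | 93.8% (5.2) |

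**Step 4: where the loss comes from, at 80%.** A 1-df trend test on the same groups isolates the cost of grouping.
- Quartiles: trend test 73.9%, so grouping costs 80 − 73.9 = 6.1 points and the unordered test a further 73.9 − 57.3 = 16.6.
- Tertiles: trend test 70.4%, so grouping costs 9.6 points and the unordered test a further 70.4 − 60.1 = 10.3.

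**Step 5: simulation.** There were 3,000 runs per setting, with exponential survival. The continuous term is linear only.

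| Effect of the marker | Mean events | Continuous | Quartiles | Tertiles |
|---|---|---|---|---|
| Log-linear, HR 1.5 per SD | 48 | 79.1% | 54.1% | 57.6% |
| Log-linear, HR 1.37 per SD | 75 | 78.0% | 54.3% | 56.0% |
| Log-linear, HR 1.5 per SD | 77 | 94.1% | 78.9% | 80.3% |
| Step in top quarter, HR 2.0 | 87 | 63.7% | 68.9% | 61.0% |
| U-shaped | 76 | 12.2% | 35.5% | 25.3% |
| None | 54 | 5.2% | 4.8% | 4.5% |

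The log-linear rows agree with Step 3 to within a few points. The step and U-shaped rows show that the advantage depends on the shape of the effect. In the U-shaped case a trend test on quartiles had only 6.4% power.

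**The case against.** The strongest objection is that much of this fills in what the plan leaves unsaid. A reader might infer that the study discards the measured concentrations throughout, or that its Cox models use quartiles. The documents support neither. The Cox sentence gives no coding at all, and the ROC analysis, which is the plan's named measure of prognostic value, would normally use the full range of values. Drawing the curves by quantile group is the natural reading but is not stated, and an unordered test is the default rather than the plan's wording. This objection stands: the calculated loss applies to the unadjusted log-rank comparison only, and it does not follow that real markers would be missed by the study as a whole.

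A second objection is that no figure for lost power can belong to this plan, because the inputs are absent. That also stands. The loss is small if the continuous test would be very well powered, and quartiles can do better than a straight line for a step or U-shaped effect.

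A third is that a spline also spends degrees of freedom. With all the information kept and a log-linear effect, an overall 2-df test (three knots) would have 70.9% power and a 3-df test (four knots) 64.5%, where the 1-df test has 80%. The spline is therefore better used as a check than as the main test.

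Finally, a reader might argue that quantile-based hazard ratios cannot be carried to other hospitals. That presupposes a grouped Cox model, which the plan does not state, and cut-points can be reported as concentrations. The Limitations section already cautions, on other grounds, against uncritical use elsewhere.

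**Conclusion.** The point holds as a cheap improvement to the analysis, not as a demonstrated defect of fixed size. The plan leaves the number of groups open, names no trend test, and does not say how a continuous marker enters the Cox model.

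It would be tempting to say that the plan costs about 20 points of power, or that grouping itself is to blame. The first is true only for a log-normal marker with a log-linear hazard and a continuous test in the 50% to 90% power range. On the second, at 80% continuous power the unordered test accounts for nearly three quarters of the quartile loss (16.6 of 22.7 points) and about half of the tertile loss (10.3 of 19.9).

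**What to change.** Amend the Statistical analysis protocol to say that:

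1. In the Cox models each continuous marker enters as log2 concentration, reported as a hazard ratio per doubling, and this 1-df term is the main test.
2. Non-linearity is checked with a restricted cubic spline whose number of knots (three or four) is fixed in advance.
3. One quantile grouping, quartiles or tertiles, is chosen now and used only for the baseline table and the Kaplan-Meier display. Any p-value on those curves comes from a log-rank test for trend.

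The cost is wording only; no further data or samples are needed. The downside is that the spline uses extra degrees of freedom, and that a step or non-monotone effect relies on it, since neither the linear term nor the trend test is suited to a U-shape.
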